9.2 Exclusion criteria

- Age < 18 years
- Atrial fibrillation, frequent ectopic beats, second or third degree atrioventricular blocks, or other conditions which might make difficult or unreliable the automatic blood pressure measurement with the oscillometric technique
- Upper arm circumference < 22 cm
- Pregnancy

10.0 PROJECT ACTIVITIES

10.1 Creation of research network and data collection

Data contained in existing electronic databases or data of newly enrolled subjects fulfilling the inclusion criteria will be uploaded/entered on the study website. These data will include ABPM measures (blood pressure and arterial stiffness) obtained with a BPLab device and clinical data. ABPM data will be provided as .bpw files or directly uploaded by linking the ABPM device to the website through a personal computer. 24-hour ambulatory blood pressure recordings will be done in accordance with the procedures described in the *Appendix 1*.

Data collection will be ensured by a dedicated web-based telemedicine platform, including an electronic case report form (e-CRF). ABPM data will be transmitted to the project website and analyzed in real-time with production of an electronic report sent by e-mail to the Investigator and available on the website. Only ambulatory blood pressure data collected with a BPLab monitor will be included in the system. The e-CRF will allow collection of patient's clinical data, such as family history, anthropometric data, habits, past and current diseases, therapies, office BP, and laboratory tests, including evaluation of target organ damage. More than one ABPM recording may be performed in the same patient if deemed necessary by the physician in charge. They will be uploaded in the telemedicine system and complemented by an update of clinical information, as mentioned above. The project does not involve any type of intervention related to the study and the physicians will manage the patients included in the registry according to the requirements of clinical practice and current guidelines. However, as recommended by current guidelines, each patient will be followed-up with visits occurring at regular intervals (ideally every 6 months, and not less than once a year). The physicians will also be free to use the ambulatory blood pressure data in the clinical management of the patients.

The telemedicine system will allow a) standardized and centralized data collection, b) data validation by experts and counselling to remote centers, c) setup and maintenance of the Registry.

10.2 ABPM data analysis

Principal derived ABPM variables and arterial stiffness measures will be calculated immediately once the data are input in the database and their adequate quality is verified. Mean blood pressure and heart rate values, PWV and AI will be computed for 24-hour, day-time and night-time by averaging the all the individual readings for the subperiod in question. Measures of blood pressure variabilities (weighted standard deviation and average real variability) will also be computed based on individual readings. Other variables of interest (e.g. nocturnal blood pressure fall, morning surge, etc.) will be subsequently defined in the framework of sub-analyses based on the registry data and calculated according to the procedures specifically defined.

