7.0 PROJECT OBJECTIVES

The specific project objectives are:

- The evaluation of non-invasive ambulatory blood pressure and arterial stiffness estimates (through PWA) in hypertensive subjects undergoing an ABPM for clinical reasons in the selected centers
- The evaluation of the changes in blood pressure and arterial stiffness estimates following treatment initiation according to current guidelines
- The assessment of the impact of non-invasive arterial stiffness estimation on target organ damage and patient's CV prognosis
- The definition of the normalcy thresholds for PWV, AI and other current and future indices derived from PWA, in hypertensive subjects, according to outcome data
- The definition of the relationship between arterial stiffness, blood pressure absolute level and blood pressure variability, and outcomes
- The setup of a worldwide network of centers performing ambulatory PWA, and the validation and promotion of the use of such technique for hypertension screening and follow-up
- The provision of evidence on the clinical relevance of non-invasive arterial stiffness assessment, in order to favor the inclusion of such evaluation in recommendations on hypertension management

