9.1 Inclusion criteria

- Male and female subjects
- Age ≥ 18 years
- Subjects referred to routine diagnostic evaluation for hypertension or established hypertensive subjects
- ABPM performed for clinical reasons with a BPLab device
- The minimum validity requirements for inclusion of the ABPM in the study are:
 - Interval between measurements not exceeding 30 minutes
 - At least 70% of expected number of readings
 - At least 20 valid readings during the day-time and 7 during the night-time
- Availability of individual measurements for ABPM on a .bpw file (BPLab format) or data directly downloaded on the telemedicine platform of the study (see below)
- Availability of basic clinical information (as detailed in Section 14.1):
- Availability of a signed informed consent form

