### 2.1 ABPM

The investigators must ensure that for any given patient and visit the ABPM is valid:

- Interval between measurement not less than 30 min
- At least 70% of expected readings
- At least 20 valid readings during the day
- At least 7 valid readings during the night

The device must always be programmed with clear indication of day-time and night-time starting time.

Special period is not managed. The (surrogate) length of the aorta must be entered in the system at the time of programming the device, by measuring the distance between jugulum and symphysis.

If .BPW files are available they can be uploaded on the website. These files must contain the information on the length of the aorta.

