### 3. ANALYSIS

The main analysis will assess:

- The general clinical characteristics of the population
- The relationship between BP and arterial stiffness and target organ damage / cardiovascular events
- The features of BP and arterial stiffness in presence of the metabolic syndrome

The following inclusion criteria will be considered:

- Male and female aged  $\geq 18$  years
- Good quality ABPM: i) at least 70% of the number of the expected readings over the 24 hours (discarded), ii) at least 20 valid measurements during the daytime and 7 during the nighttime

The parameters assessed will be:

- 24-hour average brachial SBP and DBP
- 24-hour average aortic SBP and DBP
- 24-hour average PWV
- 24-hour average aortic AI

- 24-hour wSD of SBP and DBP
- 24-hour ARV of SBP and DBP

Analysis will be done also for the day-time and night-time subperiods.

In each individual PWV will be normalized to a SBP of 100 mmHg and a HR of 60 bpm by a regression analysis of 24-hour PWV to 24-hour SBP and 24-hour HR. AI will be normalized to a HR of 75 bpm with the same procedure.

Statistical tests to be used will include analysis of variance (ANOVA) or covariance (ANCOVA) for continuous variables with adjustments for confounding factors. Discrete variables will be analyzed by Chi-square test or logistic regression analysis. Survival analysis will be carried out by Kaplan-Meier plots, log rank test and Cox regression.

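### Average real variability depends on the time between readings, but the two documents give opposite interval limits and neither makes ARV comparable across intervals

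*Protocol*

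**What the plan says.** - **Measure.** Protocol 10.2: "Measures of blood pressure variabilities (weighted standard deviation and average real variability) will also be computed based on individual readings". SAP 3 lists "24-hour ARV of SBP and DBP" among its parameters and repeats the analysis for day and night. Neither document gives an ARV formula or says how to treat gaps.
- **Use.** One objective in Protocol 7.0 is "The definition of the relationship between arterial stiffness, blood pressure absolute level and blood pressure variability, and outcomes".
- **Interval.** Protocol 9.1 requires "Interval between measurements not exceeding 30 minutes". SAP 2.1 requires "Interval between measurement not less than 30 min". The analysis-set criteria in SAP 3 do not mention the interval.
- **Completeness.** Protocol 9.1 asks for "At least 70% of expected number of readings" and "At least 20 valid readings during the day-time and 7 during the night-time". SAP 3 keeps these thresholds.
- **Source of recordings.** Protocol 10.1 admits existing databases as well as new subjects, and SAP 2.1 allows stored .BPW files to be uploaded. Recordings are to follow Appendix 1, which is provided apart and was not available here. SAP 1 says that the platform provider explains device programming to each investigator, but it states no interval.
- **Adjustment.** SAP 3 plans adjustment for confounding factors without listing them. It normalises pulse wave velocity for systolic pressure and heart rate, and augmentation index for heart rate. It has no corresponding step for ARV.

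**The concern.** Blood pressures taken close together tend to be alike. A patient recorded every 15 minutes will then show a lower ARV than the same patient recorded every 30 minutes. A missing reading has the opposite effect, because the two valid readings around the gap are further apart.

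The synopsis foresees at least 30 centres. If intervals or completeness differ between them, the resulting shift in ARV is clustered by centre and can line up with country or case-mix. An ARV difference between groups, or an ARV association with organ damage or events, could then partly reflect how the device was set. If interval is unrelated to outcome, the main effect is added noise, which weakens the association.

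**Working it through.** The documents give no expected ARV, standard deviation or autocorrelation, so there is no figure of the plan's own to reproduce. The check takes three steps.

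**1. Which intervals qualify?**

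| Interval | Expected in 24 h | 70% of expected | Protocol 9.1 | SAP 2.1 |
|---|---|---|---|---|
| 15 min | 96 | 68 | yes | no |
| 20 min | 72 | 51 | yes | no |
| 30 min | 48 | 34 | yes | yes |

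All three can meet the 20-day and 7-night minimum. Under the SAP limit alone, 20 + 7 = 27 readings cap the average interval at 1440/27 = 53 minutes, so intervals could run from 30 to about 53 minutes. If both limits bind, only exactly 30 minutes remains.

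**2. How does ARV depend on the interval?**

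Assumptions, none from the documents: Gaussian readings with within-period SD 12 mmHg (the percentages do not depend on it), a share *n* of the variance that is pure reading-to-reading noise, and exponentially decaying autocorrelation *r* at 30 minutes in the rest. Then

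E(ARV at lag t) = √(2/π) × SD × √[2(1 − ρ)], with ρ = (1 − n) × r^(t/30).

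Example with r = 0.3 and n = 0.3:
- 30 min: ρ = 0.7 × 0.3 = 0.210, so ARV = 12.0 mmHg.
- 15 min: ρ = 0.7 × √0.3 = 0.383, so ARV = 10.6 mmHg, which is 12% lower.

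Range for 15 against 30 minutes:
- With r from 0.2 to 0.5 and n from 0 to 50%, the ratio runs from 0.765 to 0.929, so ARV is about 7 to 24% lower.
- With a wider set (time constant 15 to 120 minutes, n from 0 to 100%), ARV is 14.5 to 27.1% lower with no noise, 4 to 8% lower at n = 50%, 2 to 4% lower at n = 70%, and unchanged if readings are independent.

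A simulation of 1,500 recordings per setting (time constant 45 minutes, n = 50%, night fall 15 mmHg, none missing) gave mean ARV of 10.98 mmHg at 15 minutes and 11.94 at 30 minutes, 8% lower. The shift of 0.96 mmHg is close to the sampling SD of one recording's ARV (0.98 at 15 minutes, 1.48 at 30). Mean weighted SD was 11.63 at both intervals.

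**3. What do missing readings do?**

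If 30% are missing at random, the gap to the next valid reading is k intervals with probability 0.7 × 0.3^(k−1), that is 0.70, 0.21, 0.063 and so on. In the example at 30 minutes, √(1 − ρ) is 0.889, 0.968 and 0.991 for k = 1, 2, 3. The weighted mean over all k is 0.915, and 0.915/0.889 = 1.029, so the recording's ARV rises by 2.9%. With r from 0.2 to 0.5 and n from 0 to 50%, the rise is 1.4 to 7.8%. The simulation gave about 1 to 6%. Under the wider set in step 2 the same sum runs from 0 to about 12% at 30 minutes, the top being a time constant of 120 minutes with no noise.

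Weighting each difference by its time gap does not remove the interval effect. With 30% missing, the simulated time-weighted ARV was 11.67 at 15 minutes and 12.65 at 30.

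**The case against.** The strongest reply is that the programmed interval may already be fixed. If the Protocol and SAP limits both apply, every recording is at 30 minutes. Appendix 1 may set the interval, programming is explained centrally, and the unnamed confounders could include it.

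Much of this stands. A reader might infer that centres do program differently and that the result is mistaken for patient biology. The documents do not support that: they show that it can happen, not that it does. A reader might also think the problem is the same however the 30-minute rule is worded. It is not, because if both limits bind, mixed programmed intervals disappear and only the smaller effect of missing readings remains.

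The reply does not close the point. Two opposite limits do not read as a deliberate choice of exactly 30 minutes, and SAP 3 carries neither. Instructions to investigators cannot standardise recordings made before the project. No listed covariate captures the interval.

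The size is also open to challenge, since it rests on assumed autocorrelation and falls to zero if readings are independent. That is right, and the range says so. The larger figure for a pair that straddles one missing reading (4 to 22% with r from 0.2 to 0.5 and n from 0 to 50%) should not be read as the effect on a recording, because most pairs are still adjacent.

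Finally, the variability objective does not rest on ARV alone. The weighted SD is planned in parallel, and its mean hardly moves with the interval.

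**Conclusion.** The point holds as a risk that the plan leaves open, and it is specific to ARV. The interval limits contradict each other, the analysis set has no interval rule, stored recordings are admitted, and nothing in the text makes ARV comparable across intervals.

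Under the stated assumptions, ARV at 15 minutes is 0 to about 27% lower than at 30 minutes in the same patient. A 30% random loss of readings raises a recording's ARV by about 1 to 8%. These two ranges rest on different assumption sets, wide for the first and narrower for the second. The true sizes, and whether centres differ at all, cannot be known from the documents. It deserves action because the change is cheap, not because a bias has been shown.

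**What to change.** 1. Reconcile the interval limits in Protocol 9.1 and SAP 2.1, and carry the agreed rule into the analysis-set criteria in SAP 3. Which limit is meant is for the sponsor to settle.
2. In SAP 3, give the ARV formula, including how successive readings are defined when one between them is missing.
3. Derive the actual interval (by day and night where they differ) and the number of valid readings from the stored reading times. Tabulate both by centre.
4. In every ARV model, adjust for or stratify by interval, include the number of valid readings, and account for centre. If each centre uses one interval, fixed centre effects already absorb it and a separate interval term cannot be estimated; the SAP should say which form is used.
5. As a sensitivity analysis for 24-hour and daytime ARV, use only pairs of valid readings about 30 minutes apart, where the programming allows. Recordings at 20 or 40 minutes cannot supply that lag and rely on step 4.

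The cost is SAP wording, a change to the ARV routine and a few more model terms. Reading-level data are already an inclusion requirement, so nothing new is collected.

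The common-lag ARV is noisier. At 30-minute sampling with 70% valid, about 0.7 × 0.7 = 49% of possible pairs remain. At night it may be unusable: if 7 valid readings fall at random among 16 slots (assuming 8 hours at 30 minutes), only 7 × 6/16 = 2.6 adjacent pairs are expected. That is why step 5 leaves out night ARV.

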10.3 Dissemination activities

An important part of activities in this project will be aimed at disseminating the knowledge on correct use of ambulatory blood pressure and arterial stiffness estimation in clinical practice and in research and thus at achieving a possibly standardized and widespread use of this integrated technology in the participating centers. In order to achieve these aims the project, apart from data collection, will involve the following activities:

- Exchange of knowledge between participating centers already expert in ABPM use and in arterial stiffness measurement. This will be mainly achieved by cooperation of investigators in preparing a possibly unified methodology of ABPM data collection and analysis and by jointly addressing methodological issues that may arise during the project.
- Performance of studies aimed at optimizing a possible clinical application of non-invasive ambulatory arterial stiffness estimation, based on data collected in the Registry
- Providing instructions on appropriate ambulatory arterial stiffness monitoring methodology to other physicians. Indeed, an important feature of the project will be to actively involve intermediate level centers, not necessarily expert in ABPM use and arterial stiffness determination. A major task of the consortium will be to provide these participants with an accurate information on correct methodology and interpretation of such data, in order to support them in case of difficulties and to monitor the correctness of the use of the methodology in these centers during the project
- Preparation of specific recommendations on the use and clinical application of ABPM integrated with arterial stiffness evaluation
- Cooperation with international and national scientific societies in the area related to ABPM and arterial stiffness monitoring. The majority of the VASOTENS Scientific Committee members will be selected among active members of international and national hypertension societies, including the membership in the bodies specifically dedicated to blood pressure and arterial stiffness measurement. This will facilitate the dissemination of information on the project and its findings and will also allow an interaction with writing committees involved in the preparation of guidelines pertinent to this area

11.0 STATISTICAL METHODS

Basic descriptive statistics of the entire registry with calculation of absolute and relative frequencies for categorical variables and calculation of average value, standard deviation, minimum and maximum for continuous variables will be calculated.

Standard variables (systolic and diastolic blood pressure, pulse pressure and heart rate), central systolic and diastolic blood pressure, and arterial stiffness indices (PWV and AI) will be averaged for the whole 24-hour period, and separately for the day-time and night-time subperiods. Additionally, hourly averages will be computed, and in case of blood pressure, variability will be evaluated by calculation of weighted standard deviation and average real variability.

Relationship between blood pressure and arterial stiffness estimates and organ damage and prognosis will be evaluated.

Other variables of interest will be defined in the course of the study and calculated subsequently according to the procedures defined in a specific statistical analysis plan.

The occurrence of any cardiovascular event (death or hospitalization for congestive heart failure, myocardial infarction, angina, stroke or cerebrovascular accident, renal failure, etc.) during the study will be evaluated by the Kaplan-Meier method. Time-to-event curves will be drawn and the survival analysis will be performed according to the Cox proportional hazard model, which will allow to analyze predictors of outcomes.

Analysis will be performed periodically: the first will be done at the end of the first year of follow-up of all the recruited subjects.

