### 2.2 CLINICAL DATA

That CRF must be completed with all the following information:

- Age
- Gender
- Height

- Weight
- Ethnicity
- Superficial distance between jugulum and symphysis (surrogate of aortic length) – see above
- Waist circumference
- Smoking status
- Alcohol drinking
- Coffee or tea drinking
- Dyslipidemia (yes/no and indication on treatment)
- Diabetes (yes/no and indication on treatment)
- Diagnosis of hypertension (yes/no and indication on treatment)
- Family history of premature CV disease
- Medical history, with particular regard to previous and/or concurrent CV diseases
- Office blood pressure and heart rate obtained in the same treatment condition as ABPM (only one value can be input: it could be the average of more values or just a spot measurement)
- Left ventricular mass index (LVMI) at echocardiogram
- When available, diameter of the ascending aorta assessed by the echocardiogram
- Intima-media thickness (IMT) at carotid ultrasonography
- ECG (indication on left ventricular hypertrophy, Sokolow–Lyon and Cornell index)
- When available, ankle-brachial index
- Microalbuminuria (as mg/24h) or albumin-creatinine ratio (as mg/g) and serum creatinine (estimated glomerular filtration rate – eGFR will be calculated by the software according to the Cockcroft-Gault formula)
- When available, pulse wave velocity (PWV), augmentation index (AI) and central systolic blood pressure taken during the office visit with a validated device different from BPLab Vasotens (e.g. Sphygmocor or Complior)

Additionally, this information must be recorded at any visit:

- Drug treatments: explain that in case treatments are changed or replaced the Investigator must indicate dates and status. It is not necessary to add the drug again.
- Investigators must pay attention to record at any visit both new diseases and adverse events: the latter must be recorded in the “Events” section with start and end date and all the information needed to identify the event. Priority must be given to cardiovascular events, whereas other events must be placed under the label “Other” and a description must be entered.

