### 3.1 EVALUATION OF CLINICAL CHARACTERISTICS

Evaluation and comparison of the main study parameters for the following groups:

- Males vs. females
- Young (<65 years) vs. old ( $\geq 65$  years)
- Age at risk:  $\geq 55$  years in males and age  $\geq 65$  years in females
- Ethnicity
- Smoking (smoker, no smoker, ex-smoker)
- Alcohol (yes vs. no)
- Coffee or tea (yes vs. no)
- Smoking or alcohol or coffee (yes vs. no)
- Family history for cardiovascular disease (yes vs. no)
- Previous cardiovascular diseases (yes vs. no)
- Any previous medical condition (yes vs. no)
- Arterial hypertension (untreated and treated)
- Antihypertensive treatment (yes vs. no)
- Dyslipidemia (untreated and treated)
- Lipid lowering treatment (yes vs. no)
- Diabetes (untreated and treated)
- Treatment of diabetes (yes vs. no)
- Metabolic syndrome (yes vs. no)
- Any cardiovascular disease (TIA, stroke, myocardial infarction, etc.) (yes vs. no)

Race will be modified according to the following rule in order to calculate ethnicity (missing values will be recoded into an appropriate value and if no category can be identified the “Caucasian” group will be assigned)

- Caucasian (1)
- Black (2)
- Asian (3)
- Hispanic (4)

In case of missing value for the following variables the missing value will be recoded to 0:

- Smoking
- Alcohol
- Coffee
- Left ventricular Hypertrophy at the ECG
- Family history for any CV disease
- Hypertension and therapy
- Number of antihypertensive drugs
- Dyslipidemia and therapy

- Diabetes and therapy
- Concomitant diseases and treatments
- Cardiovascular disease
- Cardiovascular risk
- Component of the metabolic syndrome and metabolic syndrome

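### Kaplan-Meier is the only incidence estimator planned for a cardiovascular composite and non-CV death is not addressed; if death means death from the listed causes, cumulative incidence is overstated, slightly early and more with long follow-up

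*Protocol*

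**What the plan says.** Protocol section 11.0, repeated in the synopsis under statistical methods, defines the outcome as "The occurrence of any cardiovascular event (death or hospitalization for congestive heart failure, myocardial infarction, angina, stroke or cerebrovascular accident, renal failure, etc". The list is left open. Its occurrence "during the study will be evaluated by the Kaplan-Meier method", and "the survival analysis will be performed according to the Cox proportional hazard model, which will allow to analyze predictors of outcomes".

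SAP section 3 has one sentence on this: "Survival analysis will be carried out by Kaplan-Meier plots, log rank test and Cox regression".

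Neither document mentions competing risks, a cumulative incidence function, cause-specific or subdistribution hazards, or a censoring rule. On data capture, SAP section 2.2 says: "Priority must be given to cardiovascular events, whereas other events must be placed under the label “Other” and a description must be entered". Neither that section nor the e-CRF list in Protocol section 14.1 has an explicit field for death or its cause.

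On timing, Protocol section 11.0 plans periodic analyses, of which "the first will be done at the end of the first year of follow-up of all the recruited subjects". Total follow-up is not given.

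**The concern.** The composite is labelled cardiovascular, and in the protocol's sentence the words for death and hospitalization both lead into the same list of causes. Read that way, a patient who dies of cancer, for example, has had no event and can no longer have one. Standard Kaplan-Meier can only treat that patient as censored, as if still at risk of a later CV event. One minus Kaplan-Meier then estimates the risk in a hypothetical setting without non-CV death, which exceeds the proportion of patients who will actually have an event.

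What is at stake is absolute risk. The registry has no upper age limit and its follow-up is open-ended. It aims to set normalcy thresholds for PWV and AI from outcome data (Protocol section 7.0) and to prepare recommendations on clinical use (section 10.3). Any published event curve, or any threshold read from such a curve, would carry the excess. The excess would also be larger in any group with higher non-CV mortality, so absolute differences between curves could be distorted.

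**Working it through.** **No figure to reproduce.** The documents give no event rate, expected number of events or cumulative incidence. All hazards below, and the 5- and 10-year horizons, are assumptions shown as a range. Only the first year is tied to a stated analysis.

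**Formulas.** Let *a* be the hazard of the CV composite, *b* the hazard of non-CV death, both constant, and *t* the time in years.

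- Limit of one minus Kaplan-Meier, with non-CV deaths censored: 1 − exp(−*a t*)
- Cumulative incidence, the target of Aalen-Johansen: [*a*/(*a*+*b*)] × [1 − exp(−(*a*+*b*) *t*)]

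**Worked case**, *a* = 0.05, *b* = 0.04, *t* = 10:

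- One minus Kaplan-Meier: 1 − exp(−0.50) = 1 − 0.6065 = 39.35%
- Cumulative incidence: (0.05/0.09) × (1 − exp(−0.90)) = 0.5556 × (1 − 0.4066) = 32.97%
- Excess: 39.35 − 32.97 = 6.38 points, or 19% relative to 32.97%

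**Range** (one minus Kaplan-Meier against cumulative incidence, with the excess in percentage points):

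| CV hazard / other death, per year | Year 1 | Year 5 | Year 10 |
|---|---|---|---|
| 2% / 1% | 1.98% vs 1.97% (0.01) | 9.52% vs 9.29% (0.23) | 18.13% vs 17.28% (0.85) |
| 3% / 2% | 2.96% vs 2.93% (0.03) | 13.93% vs 13.27% (0.66) | 25.92% vs 23.61% (2.31) |
| 5% / 4% | 4.88% vs 4.78% (0.10) | 22.12% vs 20.13% (1.99) | 39.35% vs 32.97% (6.38) |

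The relative excess is roughly *b t*/2. For *b* = 0.04 and *t* = 5 this gives 10%, against 9.9% computed. It is therefore driven by non-CV mortality and time.

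**Outside this range.** With low rates (1% and 0.3% per year) the excess is 0.04 points at year 5 (4.88% vs 4.84%) and 0.14 at year 10 (9.52% vs 9.38%). If non-CV mortality exceeds the CV rate (4% and 5% per year), it is 2.0 points at year 5 (18.13% vs 16.11%) and 6.6 at year 10 (32.97% vs 26.37%).

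**If death from any cause is a component**, no death competes with the composite. One minus Kaplan-Meier is then the right estimator and the excess is zero.

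**Hypothesis tests and regression.** Censoring non-CV deaths is exactly what a cause-specific hazard analysis does. The log-rank test then compares cause-specific hazards and Cox estimates cause-specific hazard ratios. Neither is affected by the excess above.

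**The case against.** The strongest reply is that the defect depends on a reading. There is no censoring rule, so it is an inference that non-CV deaths are censored. Death could also be read as standing alone, in which case Kaplan-Meier is correct. This stands to the extent that the point must be conditional. It does not remove the point, because the cause-specific reading is the more natural one and under either reading the plan needs a sentence to settle it.

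Second, the effect at one year is negligible and the longer horizons are not in the documents. This also stands. It is tempered by the fact that the analyses are periodic with no stated end. At the first analysis, one year is the minimum follow-up, so patients recruited early will have more.

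Third, the named purpose of the outcome modelling is to find predictors, and Cox and log-rank serve that purpose. This is correct, and the point is limited to absolute incidence.

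Two stronger readings are tempting and are not supported:

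- A reader might infer from the SAP's age grouping, "Young (<65 years) vs. old", that the bias falls unequally on age groups whose event incidence will be compared. SAP section 3.1 introduces those groups with "Evaluation and comparison of the main study parameters for the following groups". The parameters listed in section 3 are ambulatory BP, PWV, AI and BP variability, not event incidence. No Kaplan-Meier curves by age are planned.
- A reader might infer that the PWV and AI thresholds will be wrong. The documents give no method for deriving them, so this would follow only if they were set on absolute risk taken from Kaplan-Meier curves. Nor do the documents state that patients with high stiffness are older.

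**Conclusion.** The point holds in conditional form and is a minor one. Kaplan-Meier is the only incidence estimator planned for a composite labelled cardiovascular, and nothing is said about non-CV death. If death means death from the listed causes, reported incidence will be too high.

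For assumed constant hazards of 2 to 5% per year (CV) and 1 to 4% per year (other death), the excess is at most about 0.1 percentage point at year 1. It is 0.2 to 2.0 points at year 5 and 0.8 to 6.4 points at year 10. It becomes material only with long follow-up in groups with high non-CV mortality, and the documents do not say how long follow-up will be. It is zero if all-cause death is in the composite.

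**What to change.** 1. State in Protocol section 11.0 and SAP section 3 whether death in the composite is death from any cause or from the listed causes. If from any cause, Kaplan-Meier can stay as planned.
2. If cause-specific, plot and tabulate incidence by the Aalen-Johansen cumulative incidence function, with non-CV death as the competing event. Keep the log-rank test and Cox model, and label both as cause-specific.
3. Make the date and cause of every death identifiable in the existing Events section of the e-CRF. As written, a non-CV death would fall under the label Other with a free-text description.

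Steps 1 and 2 cost some wording and one standard routine, and stated incidences become slightly lower. Step 3 is a small data-capture change, best made early because causes of death are hard to recover later.
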